### Mixed effects model analysis of repeated measures

Data were collected over time on continuous variables such as vital signs, labs and medication doses. Since within participant observations are likely to be correlated, using an analytic method that accounts for the correlation is appropriate. The mixed effects modeling approach provides a mechanism for accounting such correlations. Further, the procedure can include data from participants with partially complete data, and unequally spaced measurements which are evident in the data collected. Thus, for measurements that are collected over more than two time points, the mixed effects modeling approach is used. The model chosen includes treatment, time, and time by treatment interactions. Time will be modeled as a continuous variable which is the time to actual measurement expressed as days from randomization (DAYS). The model will assume a linear relationship between response measure and time, and allow for the intercept and slope of the linear model to differ by treatment group

The model posited is:

$$\text{Response (MEASURE)} = \text{intercept} + \text{Treatment (TRT)} + \text{Time (DAYS)} + \text{Treatment (TRT)*Time (DAYS)}$$

However, the test for treatment effect in the above model tests effects at baseline which is of little value.

It is more valuable to test treatment effects after the intervention had time to affect outcomes. Accordingly, the 180 day time point is recoded to time zero as follows.

$$\text{RDAYS} = \text{DAYS} - 180$$

And fit the model:

$$\text{Response (MEASURE)} = \text{intercept} + \text{Treatment (TRT)} + \text{Time (RDAYS)} + \text{Treatment (TRT)*Time (RDAYS)}$$

The within-patient residual covariance matrix will be modeled using a compound symmetry structure, which assumes equal correlation between measurement times within a patient. The residual covariance matrix will be assumed to be the same in the two treatment groups.

Tests of fixed effects in the model will be calculated using the Kenward-Roger method for estimating denominator degrees of freedom.

To fit the model the mixed effects model below is used;

```
proc mixed data=data;
Class TRT SUBNUM RDAYSC; *RDAYSC is defined to be equal to RDAYSC;
Model MEASURE= TRT RDAYSC TRT*RDAYSC / ddfm=KR;
Repeated RDAYSC /sub=SUBNUM TYPE=CS; /Compound symmetry covariance structure/
Run;
```

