The test for treatment effect (TRT) in this model evaluates treatment effects at 180 days while the interaction term (TRT\*RDAYS) tests whether treatment effects differ over time, i.e., whether the slope (average change in measure per unit time) differs by treatment. The p-values for the treatment effect and treatment \* time interaction (when appropriate) will be reported.

If the equality of variance assumption does not hold (the variance differs a lot over time or across groups), the following code will be used. The model allows for unstructured covariance matrix.

```
proc mixed data=data method=reml;  
  class TRT VISIT SUBNUM;  
  Model Measure = TRT RDAY5 TRT*RDAYS/ solution ddfm=KR;  
  Repeated VISIT / subject=SUBNUM type=UN group=TRT;  
run;
```

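### The main PROC MIXED code in SAP Appendix 2 treats day as a factor, so its treatment and interaction tests are not the day-180 and slope tests the text describes (supportive analyses only)

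*SAP*

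**What the plan says.** The text of SAP Appendix 2 is explicit about the model. On time: "Time will be modeled as a continuous variable", measured as actual days from randomization. On shape: "The model will assume a linear relationship between response measure and time", with an intercept and slope for each arm. The SAP notes that a treatment test at baseline has little value, and so it shifts the clock: "Accordingly, the 180 day time point is recoded to time zero as follows", that is, RDAYS = DAYS - 180. After the code it states that the treatment term "evaluates treatment effects at 180 days" and that the interaction tests whether the slopes differ. Both p-values are to be reported.

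The main code, with compound symmetry, has this CLASS line and comment: "Class TRT SUBNUM RDAYSC; *RDAYSC is defined to be equal to RDAYSC". Its MODEL line is "Model MEASURE= TRT RDAYSC TRT*RDAYSC / ddfm=KR". RDAYS does not appear in it. The fallback code, for unequal variances, puts only treatment, visit and subject in CLASS and leaves day continuous.

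SAP sections 5.2 (vital signs, including heart rate), 5.4 (BNP and NT-proBNP) and 6 (drug doses) send their analyses to this appendix.

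**The concern.** Shifting time by 180 days changes what the treatment term means only if time is a number in the model. Once the day variable is in CLASS and also in MODEL, it is a set of labels. Subtracting 180 renames the labels and changes nothing else. No line is fitted, so there is no slope to compare and no time zero at which the treatment term is evaluated.

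A programmer who follows the code gets one analysis, and a reader who follows the text expects another. At stake is a mislabelled result: a treatment effect averaged over follow-up days, baseline included, reported as the effect at day 180. A second consequence is practical. SAP section 13.4 asks for verification against the plan, and here the plan contains two different models.

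**Working it through.** The plan states no figure for this analysis, so there is none to reproduce. The check compares the two models and then sizes the difference.

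**Inputs from the documents.** 104 participants enrolled (SAP 2.3), taken as 52 per arm from the 1:1 allocation (protocol 6.2). Visit windows are baseline, day 7-14, 42±14 and 180±14 (SAP 13.1). The day-90 contact is a phone call without vital signs (protocol 5.5).

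**Assumed inputs.** Effect size, trajectory, variances, missed visits, and 0-3 days from randomization to discharge. The documents give none of these.

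**1. The two models.**
- Text: mean = a + b·TRT + c·RDAYS + d·TRT·RDAYS. The arm difference on any day is b + d·RDAYS. At day 180, RDAYS = 0, so the difference is b. The interaction is one parameter, d.
- Code: one mean for each arm on each distinct day. Days seen in only one arm give no estimable arm difference. With K days seen in both arms, the default Type 3 treatment test is the equally weighted average of the K daily differences. The interaction has K - 1 degrees of freedom.

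**2. Nominal days 0, 10.5, 42, 180.** Suppose the effect grows linearly from zero to Δ at day 180.
- The coded contrast targets (0 + 10.5 + 42 + 180)/(4 × 180) = 232.5/720 = 0.32 of Δ.
- With Δ = -10 and variances of 50 between and 50 within participants, the coded estimate is -3.23. Its SE is √[(2/52)(50 + 50/4)] = 1.55. Power is about Φ(3.23/1.55 - 1.96) = 55%.
- The text model gives -10.0, SE 1.94, power above 99%.
- The coded model still contains the day-180 difference (-10.0, SE √[(2/52) × 100] = 1.96), but its treatment test does not report it.

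**3. Actual days, as the text defines time.** With visits spread evenly over the windows and none missed, there are about 72 distinct days, about 20 of them in one arm only, which leaves about 52 shared. Under linear growth the average over shared days is about 0.50 of the day-180 effect. For -8 bpm that is -8 × 0.50 = -4.0 bpm.

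**4. Dependence on trajectory.** 300 simulated trials per row; SD 8 between and 8 within participants; 12% missed visits; true effect -8 bpm at day 180; compound symmetry with known variances.

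| Assumed trajectory | Code: estimate, power | Text model: estimate, power |
|---|---|---|
| Linear growth from zero | -4.1, 50% | -8.1, 95% |
| Exponential onset, 14-day constant | -6.7, 89% | -8.5, 98% |
| Full effect at every post-baseline visit | -7.7, 96% | -8.8, 96% |

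Repeats with small differences in set-up gave 42% to 53% against 93% to 96% for linear growth, 91% against 97% for the 14-day onset, and 97% against 97% for the immediate effect.

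**5. Hand check of the last row.**
- Code: only baseline has no effect, so with K = 48 shared days the average is -8 × 47/48 = -7.8.
- Text model on the four nominal days: mean day 58.125, sum of squares 20,760, arm differences 0, -8, -8, -8 with mean -6. The slope is -8 × 58.125/20,760 = -0.0224. The value at day 180 is -6 - 0.0224 × 121.875 = -8.7.

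**6. Interaction.** With 48 shared days the coded test has 47 degrees of freedom instead of 1. Under linear growth its simulated power was 29%, against 98% for the slope test.

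**The case against.** The strongest reply is that the intended model is not in doubt. The text, the printed equation and the fallback code all treat day as continuous. RDAYSC looks like a CLASS copy of RDAYS needed only for the REPEATED statement, and the comment that defines it as itself is plainly a slip. Independent programming under section 13.4 might catch it. This stands as an account of the cause, but it does not repair the MODEL line, and the SAP offers that code as the way to fit the model.

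The reply on scope stands in full. The primary endpoint uses logistic regression (9.1). Heart rate, KCCQ and PGA use separate linear models, and heart rate below 70 bpm a chi-square test (9.2). The tertiary comparisons use chi-square and Wilcoxon tests (9.3). Section 13.6 treats analyses outside the named endpoints as exploratory, although 5.2 and Appendix 2 still call for tests.

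A reader might infer that the code loses most of its power. The documents do not support this as a property of the code, because they give no trajectory. Protocol 5.3 has ivabradine start before discharge if possible, so an early effect fits the design at least as well as slow growth. Under an immediate effect no power is lost on the treatment test, and the coded contrast (-7.7) lies nearer the assumed -8 than the linear model does (-8.8).

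A reader might also count RDAY5 in the fallback code as a further modelling error. The same line prints `TRT*RDAYS`, so a keying or text-extraction slip is the likelier explanation.

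**Conclusion.** Wrong as written, low severity. The main code in Appendix 2 does not fit the model the text specifies. Its treatment test is an average over days seen in both arms, not the day-180 effect. Its interaction is a many-degree-of-freedom test of non-parallelism, not a slope comparison. This follows from the printed lines and needs no assumption.

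The numerical consequence does need assumptions. With 104 participants, SDs of 8 and a true -8 bpm at day 180, the reported effect would be about half the day-180 effect, with about 50% power against about 94%, if the effect grows linearly. It would be about -7 to -8 bpm, with little or no power loss on the treatment test, if the effect appears early.

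The problem is confined to the repeated-measures analyses of vital signs, BNP/NT-proBNP and doses. It would be wrong to infer that the trial's endpoint results are affected, or that the analysis was in fact run this way. The documents show the planned code, not its execution.

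**What to change.** In the main code, change the MODEL line to `Model MEASURE = TRT RDAYS TRT*RDAYS / solution ddfm=KR`, with RDAYS continuous and not in CLASS. Keep RDAYSC only in CLASS and REPEATED, and correct the comment to say that RDAYSC equals RDAYS. Check that RDAY5 in the fallback code reads RDAYS.

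The cost is one line of code and one comment, recorded in a dated SAP supplement or amendment as SAP section 1 provides. The change restores the model that the text already describes, so it adds no analytic freedom. If these analyses have already been run from the printed code, they should be rerun, or the existing estimates relabelled as averages over observed days.

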## **Addendum 2 to SAP version 2.0 (Dated 11 January 2019)**

### **Modification to change calculation**

The PRIME-HF protocol (Version 3, Dated July 19, 2017 section 10.4 on page 60), specifies that change in heart rate (HR) from baseline to 180 days be calculated as (baseline heart rate – 180-day heart rate). Accordingly, the statistical analysis plan (SAP) version 2.0 specified that changes (for HR and all other measures) to be calculated as baseline line- 180 days results for all change calculations. Post database lock and treatment unblinding, a decision was made to calculate change as 180 day – baseline results so that change signs align with the direction of change (increase or decrease
